11.2.2. Montgomery-Åsberg Depression Rating Scale (MADRS)

The MADRS is a validated, 10-item, clinician-administered depression scale that has been used in clinical research since 1979 (Montgomery & Åsberg, 1979). The MADRS scale will be completed at Screening (Visit 1), Baseline (Visit 2) and after 4, 8 and 12 weeks of treatment (Visits 4, 5 and 6, respectively). The 10 items measure the core symptoms and cognitive features of clinical depression. This scale has historically been used in drug-treatment trials due to its particular sensitivity to detect treatment effects. Since there is a comparative lack of emphasis on somatic symptoms, the scale is useful for the assessment of depression in subjects with physical illness (as may be the case in subjects with PTSD).

Patients with a Screening MADRS score of > 26 may be randomized upon Medical Monitor approval, based on a review of all Screening rating scales and the patient's psychiatric/medical history.

11.2.3. Clinical Global Impression of Severity (CGI-S)

The CGI-S will be completed by an Investigator to evaluate the patient's severity at the time of the assessment. The CGI-S, status since initiation of treatment, is a key secondary efficacy endpoint in this study. The CGI-S should be completed toward the end of each in-clinic study visit, except Screening, once all of the assessments are available for the investigator's review.

11.2.3.1. CGI-S Assessments

An Investigator will complete the CGI-S assessment at Baseline, Week 4, 8 and 12 (Visits 2, 4, 5 and 6, respectively) in order to assess the overall patient severity status, and answer the following question:

Considering your total clinical experience with this particular population, how mentally ill is the patient at this time?

- 0 = Not assessed
- 1 = Normal, not ill at all
- 2 = Borderline mentally ill
- 3 = Mildly ill
- 4 = Moderately ill
- 5 = Markedly ill
- 6 = Severely ill
- 7 = Among the most extremely ill patients

11.2.4. Clinical Global Impression of Improvement (CGI-I)

The CGI-I will be completed by an Investigator to evaluate the patient's status since initiation of treatment. The CGI-I should be completed toward the end of each in-clinic post-Baseline study visit once all of the assessments are available for the investigator's review.

11.2.4.1. CGI-I Assessments

Once the patient has been randomized, an Investigator will complete the CGI-I assessment after 4, 8 and 12 weeks of treatment (Visits 4, 5 and 6 respectively) in order to assess the overall change in the patient's status since Baseline and answer the following question:

Since the initiation of treatment at Visit 2, the patient is:

- 1 = Very much improved
- 2 = Much improved
- 3 = Minimally improved
- 4 = No change
- 5 = Minimally worse
- 6 = Much worse
- 7 = Very much worse

11.2.5. Patient Global Impression of Change (PGIC)

The PGIC is a validated, self-report instrument to gauge the patient's assessment of change in condition. This form will be completed by the patient after 4, 8 and 12 weeks of treatment (Visits 4, 5 and 6 respectively). The patient will answer a single question:

Since the initiation of study medication, overall, my PTSD symptoms are:

- 1 = Very much improved
- 2 = Much improved
- 3 = Minimally improved

- 4 = No change
- 5 = Minimally worse
- 6 = Much worse
- 7 = Very much worse

11.2.6. PROMIS Sleep (short form) Scale

PROMIS refers to the Patient-Reported Outcome Measurement Information System (www.nihpromis.org), an NIH-funded initiative to develop instruments to be used across chronic conditions.

The PROMIS Sleep scale (short form 8a) will be assessed at Baseline (Visit 2) and after 4, 8 and 12 weeks of treatment (Visits 4, 5 and 6 respectively).

11.2.7. Sheehan Disability Scale (SDS)

The SDS scale is a self-report questionnaire that was designed to assess the patient's view of the degree to which symptoms have disrupted work, social life/ leisure activities, and family life/ home responsibilities during the past 1 week ([Sheehan & Sheehan, 2008](#)). In addition, the SDS asks the patient to provide the number of days or work lost as well as unproductive days in the past week. The SDS scale will be completed by the patient at Baseline (Visit 2), and after 4, 8 and 12 weeks of treatment (Visits 4, 5 and 6 respectively).

11.3. Safety Parameters

Safety will be assessed by evaluation of adverse events, responses on the C-SSRS and MADRS, clinical laboratory tests, vital signs, weight, and patient ratings of sexual function assessed by the CSFQ-14.

11.3.1. Adverse Events (AEs)

Patients will be monitored for AEs throughout the study from the time that the patient signs an informed consent and onward. AEs that are spontaneously reported, elicited or observed are to be recorded on the CRF with the date, time of onset, date and time of resolution, severity, seriousness, causality (relationship to study medication), actions required, and outcome.

To elicit AEs, non-leading, simple questions with minimal connotations should be used as the initial questions at all evaluation points during the study. Examples of these questions can be:

- How have you felt since your last visit?
- Have you had any health problems since your last visit?

If an AE occurs, the investigator will institute support and/or treatment as deemed appropriate. If a non-serious AE is unresolved on the last day of the study, an effort should be made to follow up until the AE is resolved or stabilized, the patient is lost to follow-up, or there is some other resolution of the event.

There are many symptoms associated with PTSD that can vary in intensity and frequency over time. Only symptoms that significantly worsen or become more frequent, in the opinion of the patient and outside of their normal experience, should be reported as an adverse event.

If a patient reports an oral cavity adverse event, the Investigator should examine the oral cavity to confirm the presence or absence of any irritation or other signs. Additional details related to onset, duration, severity and reversibility of the oral cavity event will be documented (Section 11.3.5).

Additional information regarding definition and reporting requirements for adverse events, serious adverse events, and pregnancies is provided in [Section 11.3.1](#).

11.3.2. Columbia-Suicide Severity Rating Scale (C-SSRS)

The C-SSRS is a questionnaire developed by researchers at Columbia University to assess suicide risk and to track suicidal ideation and behavior during clinical trials. This scale is intended to be used by individuals who have received training in its administration. The questions contained in the Columbia-Suicide Severity Rating Scale are suggested probes. Ultimately, the determination of the presence of suicidal ideation or behavior depends on the judgment of the individual administering the scale.

There are multiple versions of this questionnaire. At Visit 1, the “Baseline/Screening” questionnaire will be administered and the recall periods will be “lifetime” and “within the past 6 months” for suicidal ideation, and “within the past year” for suicidal behaviors. Patients whose responses are indicative of suicidal ideation with intent and/or plan (e.g., Type 4-5 ideation) within the past 6 months or a history of prior suicidal behavior within the past year will be excluded from participation, with recommended referral for appropriate intervention.

At all subsequent visits (Visit 2 through 6), the “Since Last Visit” questionnaire will be administered, and the recall period on this will be “since the last visit”. Note that if there has been a significant change in responses indicative of increased suicide risk, appropriate intervention should be prescribed as described below.

11.3.3. Safety Planning Intervention (SPI)

The C-SSRS is completed at every visit in order to assess for changes in suicidality during the study. As a screening and baseline entrance criterion, patients exhibiting Type 4 or 5 ideation in the past 6 months or a history of suicidal behavior in the past 12 months are not eligible for the study due to this risk and should be referred for appropriate emergency care. If a patient scores a 4 or 5 at a clinic visit following randomization, the patient should be withdrawn from the study and referred for appropriate emergency care. If a patient scores a 4 or 5 at any clinic visit, it should be reported as a serious adverse event.

If a patient scores a 2 or 3 on the suicidal ideation section of the C-SSRS at any visit (including the Screening visit), the investigator and patient should work together to implement a Safety Planning Intervention (SPI). In addition, if a post-baseline score of 2 or 3 represents a significant change from the patient’s baseline status, it should be recorded as an adverse event. The recommended SPI for this study is the plan developed by [name] and [name] which has been adopted by the U.S. Veteran’s Administration (VA) ([Stanley & Brown, 2012](#)). The VA SPI is a brief clinical intervention aimed at mitigating suicide risk. It consists of a written, prioritized list of coping strategies and sources of support that patients can use to alleviate a suicidal crisis. Sites may use an internally-developed SPI if similar in scope

and purpose to the VA SPI. Additional information and training on the implementation of an SPI will be provided prior to initiation of the study.

11.3.4. Physical Examination

A complete physical examination will be performed at Screening Visit 1 only. At a minimum, the physical examination will include the following components: HEENT (head, eyes, ears, nose, and throat), neck, chest and lungs, cardiovascular, abdomen, skin, and musculoskeletal. The physical examination may exclude rectal, genitourinary, and breast examinations.

11.3.5. Visual Examination of Oral Cavity

A visual examination of the oral cavity should be done at Screening (Visit 1), Baseline (Visit 2) and after 12 weeks (Visit 6) of treatment and/or at Early Termination. In addition to these regularly scheduled examinations, a visual inspection of the oral cavity (including the sublingual area) should be done any time a patient spontaneously reports an oral adverse event (other than transient sensory AEs such as tongue numbness, tingling or bitter taste) to confirm presence or absence of any irritation or other signs. Additional details related to onset, duration, severity and reversibility of oral events will be documented in the CRF.

11.3.6. Vital Signs, Height and Weight

Vital signs (sitting blood pressure and heart rate, temperature, and weight) will be assessed at Screening (Visit 1), Baseline (Visit 2) and after 4, 8 and 12 weeks of treatment (Visits 4, 5 and 6/Early Termination, respectively). Height will be measured without shoes at Visit 1 only. The BMI will be a derived variable, based on height and weight entries. A BMI > 40 is an exclusion criterion.

11.3.7. Electrocardiogram (ECG)

A 12-lead ECG will be performed at Screening (Visit 1) and will be reviewed by the Investigator for the purpose of excluding from participation patients who have either a history of or current evidence of clinically significant cardiac disease (e.g., significant arrhythmias or heart block, heart failure, or myocardial infarction within the past 2 years) or a QTcF at Screening $> 450\text{m/sec}$ (males) or $\text{QTcF} > 470\text{m/sec}$ (females).

The ECG interpretation by the Investigator will be recorded in the CRF as normal, abnormal but clinically insignificant, or abnormal and clinically significant. In addition, the standard ECG parameters including rhythm, heart rate, and intervals for PR (or PQ), QRS, and QTcF (Fridericia's) corrections for heart rate will be recorded.

If the Investigator has any concerns about the eligibility of a patient or wishes to confirm his/her assessment, the Investigator should consult with the medical monitor for this study.

11.3.8. Clinical Laboratory Assessments

The clinical laboratory evaluations to be performed in this trial are listed in [Table 1](#). Those marked as screening tests will be performed at screening only. All other tests will be performed at Screening (Visit 1) and after 12 weeks of treatment (Visit 6), or Early Termination. Clinical laboratory values may be repeated prior to randomization in order to confirm exclusionary levels

for TSH, ALT and/or AST values. If these values remain persistently elevated upon repeat, the patient is not eligible for randomization.

With the exception of the urine pregnancy tests or the ad hoc urine drug test required at baseline for patients washing off excluded medications (e.g., opioids, benzodiazepines, amphetamines), all clinical laboratory evaluations will be analyzed via a central clinical laboratory, and information regarding appropriate sample volume, collection tubes, sample labeling and handling, and shipment will be provided in a study manual.

A urine drug screen for drugs of abuse (including marijuana) will be collected at Screening Visit 1 and sent to the central laboratory for analysis. If the patient has a positive drug screen at Visit 1 and/or Visit 2 for anything other than marijuana, and the results cannot be explained by use of current allowable prescription medications, the patient should be excluded from the study. If the urine drug screen is positive at Visit 1 and the results can be explained by the use of current prescription medications (e.g., opioids, , amphetamines) that will be discontinued during screening, the investigator must repeat the drug screen and obtain a negative result using an in-clinic urine dipstick drug screen prior to randomization to confirm eligibility for the study. Patients with positive results for benzodiazepines at Screening will need to come back to the clinic for repeat centralized Urine Drug Screen following a minimum of one week off all benzodiazepines. And since the results of the repeat UDS must be confirmed negative prior to randomization, the Baseline visit should take place no sooner than 7 days after the patient's post-washout urine drug screen.

Each clinically significant abnormal laboratory value or other clinically meaningful abnormality should be followed until the abnormality resolves or until a decision is made that it is not likely to resolve. If such abnormalities do not return to normal within a reasonable period, their etiology should be identified and Tonix or designee should be notified. Treatment-emergent clinically significant abnormalities in laboratory values will be recorded as AEs.

Table 1: Clinical Laboratory Assessments

Clinical chemistry	Hematology
Alanine aminotransferase (ALT) ^a	Hematocrit
Alkaline phosphatase	Hemoglobin
Aspartate aminotransferase (AST) ^a	MCH concentration (MCHC)
Bilirubin (total)	Mean corpuscular hemoglobin (MCH)
Blood urea nitrogen (BUN)	Mean corpuscular volume (MCV)
Calcium	Platelet count
Chloride	Red blood cell (RBC) count
Cholesterol (total)	WBC differential
Creatine kinase (CK)	Neutrophil count (absolute and %)
Creatinine	Lymphocyte count (absolute and %)
Glucose	Monocyte count (absolute and %)
Phosphorus	Eosinophil count (absolute and %)
Potassium	Basophil count (absolute and %)
Protein (albumin and total)	White blood cell (WBC) count
Sodium	
Thyroid-stimulating hormone (TSH)^c at screening	Serum Pregnancy Test at Screening^b
Free T4 only if TSH is outside of normal limits	Urine Pregnancy Test (qualitative dipstick)^b
Human immunodeficiency virus types 1 and 2 (HIV₁ and HIV₂)	Urine Drug Screen^d
Pharmacogenomic testing (optional; can be obtained at any visit post-Screening, including an early termination visit)	

^a Level greater than 3 times the upper limit of normal is an exclusion (if persistent upon repeat).

^b Pregnancy testing for females of child-bearing potential only. A positive pregnancy test is exclusionary (Visit 1 or Visit 2) or mandates withdrawal from the study (all other visits).

^c TSH level greater than 1.5 times the upper limit of normal is exclusionary at Visit 1.

^d Urine drug screening will be conducted on all patients at Screening and, if necessary, at Baseline in patients with a positive result for opioids, barbiturates, amphetamines or oxycodone at Screening and who otherwise qualify for the study. For patients testing positive at the Screening visit for an excluded medication that will be discontinued during the screening interval, an in-clinic urine dipstick drug screen will be performed at the Baseline visit and must be negative in order for the patient to be eligible for randomization (this will primarily apply to opioids and amphetamines). Patients with positive results for Benzodiazepines at Screening will need to come in to the clinic for a repeat centralized Urine Drug Screen following a one-week drug free interval, and the Baseline Visit may need to be delayed in order to ensure that the results from the repeat centralized UDS can be confirmed negative prior to randomization.

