10.4. Visit 4 and 5 (Weeks 4 through 8)

Visits 4 and 5 are similar study visits that are scheduled to be conducted after 4 and 8 weeks of treatment, respectively. Visit 4 should occur on Day 28 ± 5 days and Visit 5 should occur on Day 56 ± 5 days.

The following assessments and procedures are scheduled for these visits in the following general order:

- Collect study drug and assess compliance
- Assess occurrence of adverse events
- Update concomitant medications
- Obtain vital signs and weight
- Administer CAPS-5-“Symptom Severity Version” using 1-week recall
- Conduct urine pregnancy test (for women of child-bearing potential)
- Have the patient complete the following outcome scales (in order):
 - SDS
 - PROMIS scale for sleep disturbance
 - PGIC
- Administer the MADRS
- Administer C-SSRS - Since Last Visit Version
- Physician to assess CGI-S and CGI-I (needs to be completed once all other assessments are available for investigator to review)
- Dispense new bottles of double-blind study medication as assigned by IWRS

After all of the assessments at each visit have been completed, the patient should be given an appointment to return to the clinic for the next scheduled visit, and be re-instructed, as necessary, on dosing instructions, and reminded to bring study medication back to the clinic at their next visit.

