10.5. Visit 6 (Week 12)

Visit 6 should occur after 12 weeks of double-blind study drug treatment, scheduled at Day 84 -5 / +7 days. The following assessments and procedures are to be completed in the following general order:

- Collect study drug and assess compliance
- Assess occurrence of adverse events
- Update concomitant medications
- Obtain vital signs and weight
- Administer CAPS-5-“Symptom Severity Version” using 1-week recall
- Conduct urine pregnancy test (for women of child-baring potential). Serum pregnancy test may be done at Investigator’s discretion.
- Draw samples for clinical laboratory tests for:
 - Chemistry and hematology
- Perform visual examination of oral cavity

- Have the patient complete the following outcome scales (in order):
 - SDS
 - PROMIS scale for sleep disturbance
 - PGIC
 - CSFQ-14
- Administer the MADRS
- Administer C-SSRS-Since Last Visit Version
- Physician to assess CGI-S and CGI-I (needs to be completed once all other assessments are available for investigator to review)

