10.5.1. Early Termination (ET)

In accordance with the Declaration of Helsinki, patients have the right to withdraw from the study at any time for any reason, and they will be advised of this right. The investigator and Tonix also have the right to remove patients from the study. Specific reasons for removal of a patient from the study could include, but are not limited to:

- An adverse event (AE)
- An illness that, in the judgment of the investigator or Tonix, might invalidate the study results or place the patient at risk
- The request of the patient, investigator, or Tonix, whether for administrative or other reasons
- Pregnancy

This study will attempt to obtain as complete information as possible on all participating patients. An effort must be made to contact the medical monitor prior to any patient's early termination. Each reason for early termination will be adjudicated. Patients who wish to terminate their participation in the study should be instructed to come to the clinic for an Early Termination Visit. The purpose of the Early Termination visit is to obtain critical information about the patient's participation, and should be scheduled preferably before there has been a substantial lapse in study medication usage. However, even if there has been a medication lapse, the patient should be encouraged to return to the clinic for this visit, and should be instructed to return all study medication. NOTE: These visit procedures are not intended for patients who fail to qualify for randomization or for any other reason withdraw from the study prior to receipt of a dose of double-blind study drug.

If the patient withdraws prior to the Week 2 (Visit 3) visit window (before Day 11), the following assessments and procedures are to be completed at this visit in the following general order:

- Document reason for early termination. The investigator should carefully assess the role of adverse events and/or lack of efficacy when determining the most accurate reason for the patient's early termination.

- Collect study drug and assess compliance
- Assess occurrence of adverse events
- Update concomitant medications
- Obtain vital signs and weight
- Conduct urine pregnancy test (for women of child-bearing potential). Serum pregnancy test may be done at Investigator's discretion.
- Draw samples for clinical laboratory tests for:
 - Chemistry and hematology
- Perform visual examination of oral cavity

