#### 7.1.2 Data Handling for Participants Who Discontinue Study Drug or Withdraw from the Study

Participants who withdraw/drop out from the study will have their ET visit data collected and included in the analysis based on the closest visit window (Week 4, 8 or 12). Visit windows will be assigned by splitting the periods between visits at the midpoint between the visits. If more than one record falls within the window, the one closest to the target date will be used in the analysis, with preference given to the scheduled visits in the case of equidistant visits.

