### **10.2 Clinical Laboratory Evaluations**

Laboratory data include analyses for Chemistry and Hematology will be summarized by treatment and visit for the Safety Population. Descriptive summaries of actual values and changes from baseline will be presented by study visit and each treatment group. 95% confidence intervals will be presented for change from baseline for each visit and last on-treatment assessment. ET data will be mapped to the closest visit window as described in

**Section 7.1.2**, but will typically only be used if a valid assessment was not collected then (scheduled visits will usually be closer to the target visit day and will take precedence if the ET and scheduled visit are equidistant to the target visit day).

Laboratory values will be displayed in the data listings and those that are outside the normal range (“H” or “L”) will be flagged, along with corresponding normal ranges. Values pre-defined as potentially clinically significant (“HH” or “LL”) will also be flagged. For each laboratory analysis, shifts in assessments of abnormality from baseline to each scheduled time point will be presented in shift tables.

A by-participant listing of all clinical laboratory data will also be provided.

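### Laboratory shift tables: early-termination samples before about Day 70 are filed under visits with no scheduled laboratory tests, so no categorical laboratory table by arm covers every patient sampled

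*Protocol*

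**What the plan says.** **When blood is drawn.** Protocol 11.3.8 states "All other tests will be performed at Screening (Visit 1) and after 12 weeks of treatment (Visit 6), or Early Termination". Appendix 1 marks chemistry and hematology at Visits 1 and 6 only, and the procedures for Visits 4 and 5 in Protocol 10.4 include neither. Protocol 10.5.1 has two sets of ET procedures, one beginning "If the patient withdraws prior to the Week 2 (Visit 3) visit window (before Day 11" and the other for exits from Day 11 on. Both include chemistry and hematology, so an early leaver who attends the ET visit does have a post-baseline result.

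**Where ET results go.** SAP 10.2 says "ET data will be mapped to the closest visit window as described in" Section 7.1.2. That section has ET data "included in the analysis based on the closest visit window (Week 4, 8 or 12" and sets the boundaries: "Visit windows will be assigned by splitting the periods between visits at the midpoint between the visits".

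**Which tables are built.** For abnormality categories, SAP 10.2 says "shifts in assessments of abnormality from baseline to each scheduled time point will be presented in shift tables". It names no shift to the last or worst post-baseline value. It also plans descriptive summaries by visit, confidence intervals for change from baseline by visit and at the last on-treatment assessment, flags in the listings for out-of-range and potentially clinically significant values, and a listing of all results by participant. Protocol 13.5 calls for laboratory values to be summarized at endpoint. Protocol 11.3.8 has clinically significant treatment-emergent abnormalities recorded as adverse events.

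**The concern.** The window rule in SAP 7.1.2 assumes that each window has a scheduled assessment for the ET value to stand in for. SAP 10.4 applies the same rule to vital signs, where it fits, because Protocol 11.3.6 schedules vital signs at Weeks 4, 8 and 12. For laboratory tests only the Week 12 window has a scheduled draw, so the rule spreads a single post-baseline sample over three windows, two of which are otherwise empty.

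The shift table is the only display in SAP 10.2 that compares laboratory abnormality categories between arms. If it leaves out early leavers, or isolates them in rows with no completers, a reader cannot see the proportion of each arm that moved from normal to abnormal among all patients sampled. The comparison then depends on who stayed in the study.

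**Working it through.** The documents state no figure on this point, so there is none to reproduce. The check applies the SAP's window rule to the Protocol's visit days.

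**Inputs**
- Visits 4 and 5 (Protocol 10.4): "Visit 4 should occur on Day 28 ± 5 days and Visit 5 should occur on Day 56 ± 5 days".
- Visit 6 (Protocol 10.5): "scheduled at Day 84 -5 / +7 days".
- Midpoint boundaries: SAP 7.1.2.
- Planned size: 250, 125 per arm (SAP 5).
- Dropout rate and timing: not given in the readable text. Assumed here as 10-30%, with timing from front-loaded to back-loaded.

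**Window boundaries**
- Week 4/8: (28 + 56)/2 = Day 42.
- Week 8/12: (56 + 84)/2 = Day 70.

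Only ET samples from about Day 70 on are filed under Week 12. Earlier ones go to Week 4 or Week 8.

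**Share of ET samples outside the Week 12 window.** With F(t) the cumulative distribution of exit times over Days 0-84, the share is F(70)/F(84).

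| Assumed exit timing | Calculation | Share |
|---|---|---|
| Front-loaded, half-life 14 days | (1 − 2^−5)/(1 − 2^−6) | 98.4% |
| Front-loaded, half-life 28 days | (1 − 2^−2.5)/(1 − 2^−3) | 94.1% |
| Front-loaded, half-life 42 days | (1 − 2^−5/3)/(1 − 2^−2) | 91.3% |
| Uniform | 70/84 | 83.3% |
| Back-loaded, F proportional to t² | (70/84)² | 69.4% |
| Back-loaded, t³ | (70/84)³ | 57.9% |
| Back-loaded, t⁴ | (70/84)⁴ | 48.2% |

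**Patients affected, N = 250, uniform timing, every dropout sampled**
- 10% dropout: 250 × 0.10 × 0.833 = 20.8
- 20% dropout: 250 × 0.20 × 0.833 = 41.7
- 30% dropout: 250 × 0.30 × 0.833 = 62.5

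If only half the dropouts give an ET sample, these become 10.4, 20.8 and 31.2. With full sampling, the spread over the timings in the table is 25 × 0.482 to 25 × 0.984 (12 to 25 patients) at 10% dropout, and 75 × 0.482 to 75 × 0.984 (36 to 74) at 30%.

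**What happens to these samples in the shift tables**
- If scheduled time point means the laboratory schedule, the only post-baseline column is Week 12, and ET samples before about Day 70 are not in it.
- If it means the study visits, those samples appear in Week 4 and Week 8 rows. No continuing patient has a planned draw there, so the rows consist almost entirely of dropouts.

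On neither reading does one shift by arm include everyone with a post-baseline draw.

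**The case against.** A reader might infer that most dropouts' abnormal results disappear from the tables. The documents do not support that. ET values stay in the by-visit summaries and in the flagged listings. They also enter the last on-treatment change-from-baseline intervals if the draw counts as on-treatment. Clinically significant abnormalities are recorded as adverse events, so they reach the by-arm adverse-event tables and, where they led to stopping study drug, the discontinuation table (SAP 10.1 and 10.1.1). Only the shift tables are in question.

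Even there, exclusion is one reading of an undefined phrase. The preceding paragraph of SAP 10.2 sets out how ET data are used, and its evident purpose is to keep them. If the time points are study visits, nothing is lost. ET samples from about Day 70 reach the Week 12 column on either reading.

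The size is also assumed. Whether most ET samples are affected depends on exit timing, and at the back-loaded end of the range it is slightly under half. Patients lost to follow-up, a category in SAP 7.1.3.1, would usually give no ET sample. Nor do the documents show that laboratory signals concentrate in early leavers. That is a reasonable expectation, not a documented fact.

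These points limit the concern but do not remove it. The last on-treatment intervals describe change in value rather than abnormality category. On-treatment is not defined for laboratory data, while Protocol 10.5.1 encourages the ET visit even after a medication lapse. The flags are specified for listings, not for a comparison by arm. The adverse-event route takes only abnormalities judged clinically significant. Keeping the samples in dropout-only rows still leaves no table covering both arms in full.

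**Conclusion.** The mismatch is real and confined to the categorical laboratory display. With one post-baseline draw per patient, the window rule either removes ET samples before about Day 70 from the shift tables or separates them from the rest of their arm. The boundaries at Days 42 and 70 follow directly from the documents. The size does not: 48-98% of ET samples outside the Week 12 window rests on assumed exit timings, and about 21-62 of 250 patients rests on 10-30% dropout, uniform timing and full ET attendance. For that timing the count is a ceiling, since incomplete attendance lowers it.

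This should be corrected before table shells are programmed, because the current text performs worse than a last-value shift on either reading. It is a safety-reporting point. Alpha, power, sample size and the primary result are unaffected.

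**What to change.** In SAP 10.2, add a post-baseline time point, Week 12/ET (last post-baseline draw), presented by arm. Use it for the shift tables and for the endpoint summary that Protocol 13.5 calls for. State that it takes each patient's last post-baseline result, including ET samples, so that inclusion does not turn on the undefined term on-treatment. Keep scheduled Week 12 alone as a supporting row, and say explicitly which time points the shift tables contain.

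The cost is SAP wording and table shells. No extra samples are needed. The drawback is that the pooled row mixes patients with a few days' exposure and patients with 12 weeks. The supporting row shows the full-exposure result separately.
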